# SYNOPSIS

## **Study Purpose**

The purpose of our study is to assess the effectiveness and acceptability of a proactive screening outreach program on colorectal cancer screening rates for eligible patients at the Flatbush Family Health Center.

## **Primary Objective**

The primary objective is to compare the effectiveness of a strategy of proactive invitation (eligibility assessment followed by a mailed invitation program and navigation) vs. standard-care colorectal cancer screening at the Flatbush Family Health Center.

## **Secondary Objectives**

The secondary objective is to identify potential barriers and facilitators to the implementation of a proactive outreach colorectal cancer screening program by performing quantitative surveys and qualitative interviews of randomly selected sample of providers and patients.

## **General Design Description**

Randomized, controlled, non-blinded study

## **Study Date Range and Duration**

The estimated duration for the study is approximately one year from the start of the intervention period (anticipated November 2022 – November 2023, depending on all approvals and other factors outside of the control of the study team).

## **Number of Study Sites**

There is 1 study site for this project: Flatbush Family Health Center at NYU Langone

## **Primary Outcome Variables**

The primary outcome variable is completion of initial fecal immunochemical test (FIT) or colonoscopy at 6 months.

## **Secondary and Exploratory Outcome Variables**

Secondary outcome variables include:

- 1) Completion of colonoscopy for individuals with a positive fecal immunochemical test at 6 months.
- 2) Determination of factors associated with non-adherence to initial fecal immunochemical testing or colonoscopy, and to completion of colonoscopy for those with positive FIT.

### Study Population

The study population will be individuals aged 45-75 years old who receive medical care at a federally qualified health care center in Brooklyn, New York whom are either due or overdue for colorectal cancer screening.

### Number of Participants

There will be a total of 100 participants in the study, 50 of whom will be randomized to receive proactive screening outreach and 50 of whom will be randomized to receive usual care.

### Study Flow Chart

	QTR 1	QTR 2	QTR 3	QTR 4	QTR 5	QTR 6
Develop tailored invitation and other study letters; develop process for FIT mailings and returns; Work with FHC to establish process for training staff; IT support for obtaining list of screen eligible individuals and electronic data capture; Develop Protocol; Develop qualitative interview guides; Set up database for data entry in REDCap; IRB approvals	X	X				
Perform the screening program at FHC		X	X	X	X	
Study accuracy of organized screening program and logistical aspects				X	X	
Perform physician and patient qualitative interviews				X	X	X
Collect data on screening rates and perform analyses as planned and dissemination					X	X

## ABBREVIATIONS

Abbreviation	Explanation
CRC	Colorectal Cancer
EMR	Electronic Medical Records system
FHC	Family Health Center
FIT	Fecal immunochemical test

# **1 - Statement of Compliance**

## **1.1 Statement of Compliance**

This document is a protocol for a human research study. The purpose of this protocol is to ensure that this study is to be conducted according to the Common Rule at 45CFR46 (human subjects) and other applicable government regulations and Institutional research policies and procedures.

## 2 - Background

### 2.1 Background

Colorectal Cancer (CRC) is the third most common cancer in men and women and the second leading cause of cancer related death. Screening for CRC reduces CRC incidence and mortality, and is recommended for average risk men and women between the ages of 45 and 75 by the US Preventive Services Task Force guidelines; which were updated recently to include 45-49 year olds, an additional 20 million individuals in the US. In New York State, CRC screening rates are over 70% but only 48-52% in Brooklyn family health centers (FHC) that provide free and subsidized health services to underrepresented minorities. Currently, invitations to screen are offered only when a patient is seen by his or her provider. Consequently, many eligible individuals, particularly 45-55 year olds who do not regularly access healthcare are underscreened.

## 3 - Rationale/Significance

### 3.1 Problem Statement

CRC screening rates are 72% in New York State but 48-55% in the federally qualified health center where we anticipate performing the study. Hence, there is an unmet need to organize and implement CRC screening using multilevel interventions to improve screening rates.

The current model for CRC screening is far from optimal and poses many barriers at the patient, provider and systems level. At the patient level: the current model requires an in-person or telehealth visit, which poses barriers through difficulty accessing transportation, time commitments and financial barriers. Furthermore, men and women aged 45-55 (on the younger end of the screening spectrum) may not have a primary care provider or seek routine medical care. Many individuals may not know they are eligible for CRC screening or the benefits of CRC screening. At the provider level, barriers include lack of up to date information and a lack of time to address CRC screening in a short clinic visit with many pressing urgent medical needs. The alternative method of screening we are proposing, an organized program of proactive invitation, has two main components: 1) *identification* of screen eligible individuals using health records from the clinic; and 2) a *proactive invitation* program, with (a) mailed invitation, (b) a package of materials so patients can complete a fecal immunochemical test (FIT) from their homes (i.e., FIT kit), and (c) instructions on how to schedule colonoscopy if they prefer this to completing the FIT. From a public health perspective, an outreach screening program is more likely to reach all individuals eligible for screening.

Multiple trials have reported higher screening rates with proactive invitation through outreach efforts and programmatic approaches, compared to usual care. Kaiser Permanente Northern and Southern California implemented proactive outreach screening in 2008, based primarily on annual FIT. Their reported rates of CRC screening are one of the highest in the country, at 81%. In their recent publication, they reported that 323,349 health plan members were reached through the program. Completion rates for screening improved from 48% to 86% over 4 rounds of implementing the outreach screening process. The program detected 80% of patients diagnosed with stage I colon cancer within 1 year of screening.

### 3.2 Purpose of Study/Potential Impact

Disparities exist in the CRC screening rates in the Brooklyn family health centers compared to New York State at large, likely driven primarily by social determinants of health. The purpose of this study is to establish the effectiveness of a proactive CRC screening outreach approach on improving CRC screening rates in an underserved population. We will also gather data regarding patient and provider perception of feasibility and overall experience with the proactive outreach program in order to better inform future screening implementation efforts. Ultimately, the broader goal is to decrease patient morbidity and mortality from CRC through improved screening rates.

### 3.3 Potential Risks and Benefits

#### 3.3.1 Potential Risks

Potential risks of the study include psychological harm associated with potential false-positive results on FIT screening or rare adverse reactions to routine colonoscopy screening which may include bleeding, bowel perforation, or adverse reactions to anesthesia during colonoscopy.

There is also a risk of loss of confidentiality. To protect participant confidentiality, the records from the study will be kept private. Any published reports will not include any information that can be used to identify individuals. Research records will be stored securely and only the study team will have access to the records. The recordings from interviews will only be accessible to the study team and a professional transcription service. The transcriptions of the recordings will have all identifying information removed. The recordings will be destroyed at the end of the study. De-identified information from the interviews will be provided to Flatbush FHC for the purpose of improving their colorectal cancer screening program.

### **3.3.2 Potential Benefits**

Potential benefits to subjects include improved access to CRC screening, earlier detection of CRC, and decreased morbidity and mortality associated with CRC. On a larger scale, potential benefits to society at large include further proof of concept of the efficacy of proactive outreach programs for increasing CRC screening rates amongst underserved populations. CRC is the third most common cancer in men and women as well as the second leading cause of cancer related death. Given that CRC screening is associated with decreased morbidity and mortality, the benefits of improving screening rates far outweigh any potential risks associated with our study.

## 4 - Study Objectives

### 4.1 Hypothesis

We hypothesize that CRC screening rates will improve in underserved populations with the implementation of a proactive approach that incorporates a mailed *outreach invitation* to screen with fecal immunochemical testing (FIT), followed by active assistance to colonoscopy completion if preferred or indicated by FIT test result.

### 4.2 Primary Objective

The primary objective is to compare the effectiveness of a strategy of proactive invitation (eligibility assessment followed by a mailed invitation program and navigation) vs. standard-care CRC screening at Flatbush Family Health.

### 4.3 Secondary Objectives

The secondary objective is to identify potential barriers and facilitators to the implementation of a proactive outreach CRC screening program by performing quantitative surveys and qualitative interviews of a randomly selected sample of providers and patients. These data can be used to inform further tailoring of an ongoing program of proactive CRC screening at this clinic, if shown to be feasible and effective.

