## 5 - Study Design

### 5.1 General Design Description

Our study is a single-site randomized, compared effectiveness study. Patients randomized to the proactive outreach group will be blind to the presence of an alternative group assignment. Patients randomized to the usual care group will be blind to the presence of group assignment altogether. Group allocation will be concealed because all patients will be randomized at a single time point. To accurately assess whether this proactive approach is effective, real-world, unbiased behavior by the patients involved is vital. Intervention group patients will be informed that their data will be used for this research project via a study information sheet included with the initial FIT kit mailing. This sheet will clearly indicate that the CRC screening itself is standard of care screening for which they are due and not a research test. We are seeking a waiver of HIPAA authorization, a complete waiver of consent for the usual care group, and a waiver of documentation of written consent for the intervention group, including the subset of intervention patients who complete the post-intervention interview. This subset will be verbally consented via telephone prior to completing the interview.

The study team will operate mainly in the background, to facilitate mailings and reminders. All materials will be sent on behalf of the clinic, using the clinic's usual stationery, and containing the electronic signature of the patient's primary care physician, when applicable. The study team will be tracking the cost and effort involved to help the clinic determine the feasibility of long-term implementation of a proactive screening program for CRC.

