#### **5.3.1 Number of Participants**

There will be a total of 100 participants in the study, 50 of whom will be randomized to receive proactive screening outreach and 50 of whom will be randomized to receive usual care.

Approximately 7 patients from the intervention group are expected to complete a follow-up interview about their experience with the proactive program.

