After the intervention period is over, patients in the intervention group will be invited to complete a qualitative interview with a trained member of the study staff, during which they will be asked about their personal experience with the proactive outreach screening program. An invitation letter will be mailed and non-responders will receive a follow-up phone call or text message to gauge interest in participating. Those who agree will be verbally consented over the phone prior to the interview.

Patients need not have completed the at-home screening to take part in the interview. Interviews will be audio recorded and professionally transcribed, with all identifiers scrubbed from the transcription.

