## **7.7 Study Records**

Study records include subject medical records including FIT testing/colonoscopy results, outreach attempts and outcomes, and any survey results collected and interview transcripts.

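### The two-sample t-test does not serve either secondary outcome, the denominator for colonoscopy after a positive FIT is contradictory, and the provider and survey parts of the secondary objective have no procedures

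*Combined protocol and SAP*

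**What the plan says.** **Objective.** Section 4.3 promises "quantitative surveys and qualitative interviews of a randomly selected sample of providers and patients", and the Synopsis says the same ("qualitative interviews of randomly selected sample of providers and patients"). Section 3.2 intends to learn about "patient and provider perception of feasibility and overall experience with the proactive outreach program". The Study Flow Chart has a row "Perform physician and patient qualitative interviews", and Section 7.7 lists "any survey results collected and interview transcripts" among the records.

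**Procedures.** Section 5.3.1: "Approximately 7 patients from the intervention group are expected to complete a follow-up interview". Section 6.1.1 describes the approach to intervention patients: "An invitation letter will be mailed and non-responders will receive a follow-up phone call or text message". Section 6.3.2 gives verbal consent for those who opt in, Section 6.3.6 limits interviews to a subset of the proactive arm, and the consent route in Section 5.1 covers "the subset of intervention patients who complete the post-intervention interview".

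**Secondary outcomes.** Section 5.2.2 lists (1) completion of colonoscopy by 6 months in those with a positive FIT, and (2) factors associated with non-adherence to initial screening and to colonoscopy after a positive FIT.

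**Analysis.** Section 6.2.1 compares outcome 1 between arms among FIT-positive patients. Sections 6.4.1 and 6.4.3 apply the intent-to-screen principle to all participants for the same outcome. Section 6.3.7 makes the 50 patients mailed a kit the denominator for the rest of the study. Sections 6.4.1 and 6.4.3 attach the t-test to the primary outcome and outcome 1; Section 6.4.3.2 repeats it for the secondary objectives. No other inferential method is named, and no factors are listed for outcome 2.

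**The concern.** For outcome 1, a reader cannot tell whether the rate is out of FIT-positive patients or out of everyone randomized, and the two answer different questions. If it is FIT-positive patients, there will be very few, and who they are depends on the intervention: only the outreach arm is mailed a kit (Section 6.1.4). A difference between arms in that subset is not protected by randomization.

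For outcome 2, a between-arm t-test answers no question about factors. Turned round to compare completers with non-completers, it still cannot take a factor with several categories, such as the race and ethnicity fields in Section 6.3.4, and it cannot account for arm. With neither factors nor a fitting method named, both could be chosen after the data are seen.

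For the objective, mention of providers, surveys and random selection claims a reach that the procedures do not provide. Section 4.3 says the results may shape the clinic's ongoing program, so readers need to know whose barriers were heard.

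**Working it through.** **The plan's own figures.** The sample size is set by feasibility (Section 6.4.2), with no alpha, power or effect size, so there is no power figure to reproduce. The arithmetic agrees: 50 + 50 = 100. Interviews cover 7/50 = 14% of the intervention arm. The number of providers or survey respondents specified is zero.

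**Outcome 1, FIT-positive denominator.** The documents give neither FIT uptake nor positivity for this population, so both are assumptions.
- Expected positives per arm = 50 × uptake × positivity. Low end: 50 × 0.10 × 0.04 = 0.2. High end: 50 × 0.50 × 0.10 = 2.5.
- A middle case has uptake of 50% (outreach) and 20% (usual care), with 7% positivity. Expected positives are 50 × 0.035 = 1.75 and 50 × 0.014 = 0.70. P(no positive in an arm) is 0.965^50 = 0.168 and 0.986^50 = 0.494. P(at least one arm has none) = 1 − (1 − 0.168)(1 − 0.494) = 0.58. P(both arms have at least 2) = 0.08.
- Smallest two-sided Fisher p when every patient in one arm completes and none in the other does: 0.33 for 2 v 2, 0.10 for 3 v 3, 0.029 for 4 v 3. At an assumed 0.05 level, nothing up to 3 v 3 can be significant.
- The t-test at 2 v 2 rejects only when neither arm has any variation. If those cases count as rejections, its type I error is 12.5% at a true completion rate of 0.5.

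**How often the t-test cannot be computed.** It needs a positive in each arm, at least 3 in total, and some variation within an arm. With kits split evenly and colonoscopy completion of 50% (assumed):

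| Kits returned (total) | Positivity | P(not computable), FIT-positive denominator |
|---|---|---|
| 10 | 4% | 99.7% |
| 30 | 10% | 63% |
| 50 | 10% | 31% |

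**Outcome 1, 50-per-arm denominator.** The test fails only if nobody has a colonoscopy after a positive FIT: (1 − 0.04 × 0.5)^10 = 0.82 for 10 kits at 4%, and (1 − 0.10 × 0.5)^30 = 0.21 for 30 kits at 10%.

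**Outcome 2.**
- Two-level factor, 25/50 v 15/50: t-test p = 0.0416, uncorrected chi-square p = 0.0412. The 0/1 scale is not the difficulty.
- Precision at n = 100, unadjusted, factor present in 50%: the 95% CI for an odds ratio extends by a factor exp(1.96 × √(sum of 1/cell)) either side. With 20 completers (cells 10, 10, 40, 40), exp(1.96 × √0.25) = 2.7. With 40 completers (cells 20, 20, 30, 30), exp(1.96 × √0.1667) = 2.2.

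**Objective against procedures.**

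| Element promised | Where a procedure is given |
|---|---|
| Patient interviews | Sections 5.3.1, 6.1.1, 6.3.2, 6.3.6: intervention arm, opt-in |
| Provider interviews | Timeline row and purpose statement only; no number, selection or consent |
| Surveys | Records list only; no instrument, timing or respondents |
| Random selection | No draw of interviewees described |

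**The case against.** This is a pilot sized on feasibility, and low precision is accepted from the start. That is fair, but it does not excuse a contradictory denominator or an outcome without a fitting analysis.

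Intent-to-screen can be read as settling the denominator at 50 per arm. The comparison then keeps the protection of randomization, and the t-test can be computed more often. This stands as a possible reading. It turns outcome 1 into a composite of returning a kit, testing positive and having the colonoscopy, which is not what Sections 5.2.2 and 6.2.1 describe.

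A reader might infer that the outcome 1 test almost never runs. The documents do not support that: the probability rests on assumed uptake, positivity and completion, and on the choice of denominator. It ranges from near certainty down to 31% on one reading and 21% on the other.

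A reader might also infer that a t-test on yes/no data is invalid in itself. It is not: with 50 per arm its type I error is 0.048 to 0.050 at true rates of 10% and 30%.

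Nor does leaving out arm wreck outcome 2. Take a factor with 30% prevalence and a chance imbalance of 1.96 × √(2 × 0.3 × 0.7/50) = 18 points (39% v 21%), with completion of 50% v 30% (assumed). Crude completion is then 0.430 v 0.387, a shift of about 4 points.

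Finally, opting in does not contradict random selection. Section 6.1.1 can be read as inviting the whole intervention arm, which was itself assigned at random. The missing draw is therefore a minor point; the missing provider and survey procedures are not. Interviews are already open to patients who did not complete screening, and the plan does not claim to estimate how common each barrier is.

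**Conclusion.** The point holds in three parts, all confined to secondary aims.

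(a) Outcome 1 has a contradictory denominator. If it is FIT-positive patients, about 0.2 to 2.5 per arm are expected under 10–50% uptake and 4–10% positivity, both assumed. They are a subset shaped by the intervention. The planned t-test would give no reliable between-arm result and often could not be computed. The contradiction itself needs no assumption.

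(b) Outcome 2 has no fitting analysis. The defect is that factors are not named, factors with several categories cannot be handled, and arm is ignored. It is neither the yes/no scale nor a large bias.

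(c) Providers and surveys are promised without selection, instruments or consent; what is planned is about 7 volunteer patient interviews, 14% of one arm.

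The primary comparison is unaffected.

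**What to change.** 1. **Outcome 1.** State one denominator in Sections 6.2.1, 6.3.7, 6.4.1 and 6.4.3. Report colonoscopy after a positive FIT by arm as x of n FIT-positive, with the number randomized beside it and exact 95% CIs, and no t-test. Treat the second half of outcome 2 the same way, and align Section 6.4.3.2.
2. **Outcome 2.** Replace the t-test with an exploratory logistic model of non-completion of initial screening, using a few pre-named terms: arm, age and sex, the last two being the randomization strata in Section 6.1.2. Say in advance which terms drop out if the smaller outcome group is sparse. Cross-tabulate other factors, such as race, ethnicity and smoking status, by arm. Give 95% CIs and make no significance claims. The exact threshold for dropping terms is for the sponsor to choose.
3. **Objective.** Reconcile the Synopsis, Study Flow Chart and Sections 3.2, 4.3 and 7.7 with Sections 5.3.1, 6.1.1, 6.3.2 and 6.3.6. Either limit the objective to descriptive interviews with volunteer intervention patients, reporting numbers invited and interviewed by screening-completion status, or keep providers and surveys and add their selection, instruments and consent.

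**Cost.** An amendment with IRB approval (Sections 7.2 and 7.13, Study Modification), mostly wording, one analysis paragraph and a tally of interview invitations. No extra patients are needed. The price is no between-arm test for outcome 1, wide intervals for outcome 2 at n = 100, and either a more modest objective or the work of writing the provider and survey procedures. Interviewees remain volunteers.

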## 5 - Study Design

### 5.1 General Design Description

Our study is a single-site randomized, compared effectiveness study. Patients randomized to the proactive outreach group will be blind to the presence of an alternative group assignment. Patients randomized to the usual care group will be blind to the presence of group assignment altogether. Group allocation will be concealed because all patients will be randomized at a single time point. To accurately assess whether this proactive approach is effective, real-world, unbiased behavior by the patients involved is vital. Intervention group patients will be informed that their data will be used for this research project via a study information sheet included with the initial FIT kit mailing. This sheet will clearly indicate that the CRC screening itself is standard of care screening for which they are due and not a research test. We are seeking a waiver of HIPAA authorization, a complete waiver of consent for the usual care group, and a waiver of documentation of written consent for the intervention group, including the subset of intervention patients who complete the post-intervention interview. This subset will be verbally consented via telephone prior to completing the interview.

The study team will operate mainly in the background, to facilitate mailings and reminders. All materials will be sent on behalf of the clinic, using the clinic's usual stationery, and containing the electronic signature of the patient's primary care physician, when applicable. The study team will be tracking the cost and effort involved to help the clinic determine the feasibility of long-term implementation of a proactive screening program for CRC.

